5.7. Analysis Visit Windows

Unless otherwise specified, data will not be analyzed using visit windows; instead, nominal visits will be used. Each visit per study schedule will be mapped to analysis visit for summary tables. Early termination visits will be mapped to next schedule visit and summarized.

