## 6.2 Treatment Period

The first shipment will contain sufficient medication for the first 4 weeks of the study, after which, two more shipments will be triggered for ongoing treatment based on participant response and PI or designee's prescription.

Once study medication is received, the participant will confirm receipt and administration of the first dose within the study mobile app. At all other timepoints, dosing information will be captured during the televisit.

A televisit will be scheduled 4 weeks (28 days), 9 weeks (63 days ) and 14 weeks (98 days) after date of first dose ([Table 1](#), [Figure 1](#)). Participants will need to continue to take study medication as per the instructions provided by the Investigator during the Treatment Period.

	Protocol 812P413	
	Page 26 of 61	Version 2.0

During the Televisit #2 and #3 (Weeks 4 and 9), the following will be administered, obtained or collected by a qualified/trained rater or assessor (ClinRO efficacy assessments should not be administered if participant is discontinuing and has not taken daily dose of Qelbree for >7 consecutive days prior to the televisit):

- AISRS
- CGI-S
- CGI-C
- C-SSRS '*Since Last Visit*' Version
- Review AEs
- Review Concomitant Medications
- Report systolic/diastolic blood pressure, pulse rate, and weight
- Report UPT results (FOCPs only)
- RMCH Questionnaire's Menstrual-Question #5 (FOCPs only)
- SM accountability; Report the number of remaining capsules in bottle
- Confirm or reschedule next virtual visit (Week 9 and Week 14, as applicable)

In addition, at Weeks 4 and 9, the participant will complete the following via the study mobile app (PRO efficacy assessments should not be administered if participant is discontinuing and has not taken daily dose of Qelbree for >7 consecutive days prior to attempting them):

- SM administration mode/time query; report admin method and average admin time
- ASRSv1.1-SC
- PHQ-8
- GAD-7
- WPAI:SHP

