### 6.3 End of Study

During the Televisit #4 (Week 14/EOS), the following will be administered, obtained or collected by a qualified/trained rater ([Table 1](#); ClinRO efficacy assessments should not be administered if participant has not taken daily dose of Qelbree for >7 consecutive days prior):

- AISRS
- CGI-S
- CGI-C
- SIGMA

	Protocol 812P413	
	Page 27 of 61	Version 2.0

- SIGH-A
- C-SSRS '*Since Last Visit*' Version
- Review AEs
- Review Concomitant Medications
- Report systolic/diastolic blood pressure, pulse rate, and weight
- Report UPT results (FOCPs only)
- RMCH Questionnaire's Menstrual-Question #5 (FOCPs only)
- SM accountability; report the number of remaining capsules in bottle
- Schedule safety follow-up televisit

In addition, at Week 14/EOS, the participant will complete or report the following via the study mobile app (efficacy assessments should not be administered if participant has not taken daily dose of Qelbree for >7 consecutive days prior):

- SM administration mode/time query; report admin method and average admin time
- ASRSv1.1-SC
- PHQ-8
- GAD-7
- WPAI:SHP
- PSQI
- BRIEF-A

If participant discontinues early (Early-Termination), perform Week 14 assessments; however, ClinRO/PRO efficacy assessments should not be administered if participant has not taken daily dose of Qelbree for >7 consecutive days prior.

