## 10.2 Study Discontinuation

The participant may withdraw themselves from the study at any time by notifying the study team. Participants may be discontinued from the study by the Investigator or designee if study procedures have not been followed or if the Investigator or designee determines the participant is not able to safely continue with the study due to an AE or other health-related issue.

Reasons for participant's study discontinuation may include:

- Withdrawal of consent (the reason for withdrawal of consent should be captured)
- Adverse event(s)
- Lack of efficacy
- Noncompliance with study procedures
- Lost to follow-up (the Investigator will document efforts to attempt to reach the participant by phone, email, and chat via study mobile app prior to considering that participant lost to follow-up)
- Other

After a participant has been discontinued, they will not be allowed to re-screen for enrollment in the study, unless there is a technical issue. The reasons for discontinuation will be documented in the participant's study record. Participants enrolled in error may be discontinued from the study with agreement from the Investigator and Sponsor.

If a participant is discontinued for any reason other than lost to follow-up, Week 14 procedures should be completed, and any outstanding data recorded in their record. If a participant is withdrawn at any stage during the study due to an AE, the Investigator or designee will advise the participant of appropriate follow-up with a local doctor, if needed. If a participant's involvement in the study ends prior to resolution of an event, the event will be marked as ongoing and the Investigator or designee will advise the participant of appropriate follow-up (e.g., to provide follow-up information/referral to the participant's primary care physician). The status of the AE at the last follow-up will be documented. The reason for discontinuation and efforts to follow participants who discontinue because of AEs will be fully documented.

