4.3. Exploratory Efficacy Variables

5. STATISTICAL CONSIDERATIONS

5.1. General Statistical Methods

All statistical analysis will be performed using SAS version 9.4 or higher. All statistical analyses will be presented using descriptive statistics. Summary statistics for continuous variables will include sample size (N), mean, median, standard deviation, interquartile range (Q1 and Q3), minimum, and maximum. Standard error may be added if it is needed for the display and interpretation of some efficacy results. Summary statistics for categorical variables will be presented in terms of frequencies and percentages. Participant data listing to support summaries will be provided.

Unscheduled measurements (unless defined as baseline or otherwise specified) will be excluded from descriptive statistics performed by visits in summary tables but will be included in data listings and other analyses that not performed by visit. For assessments that are repeated, unless otherwise specified, the non-missing values from the first assessment will be used for generating summary statistics.

Mean (\pm SE) profiles and Mean (\pm SE) CFB for AISRS total score, MADRS, HAM-A and GAD-7 will be plotted by visit.

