7.2. Secondary Efficacy Analysis

The following secondary endpoints will be analyzed in a similar manner to the primary endpoint. A comparison of Week 14/EOS vs Baseline difference in CFB with a nominal p-value from one sample t-test and associated 95% CI for any of the secondary endpoints may be explored as needed.

- CFB in AISRS Inattention Subscale score by visit
- CFB in AISRS Hyperactivity/Impulsivity Subscale score by visit
- CFB in ASRSv1.1-SC Total score by visit
- CFB in ASRSv1.1-SC Inattention Subscale score by visit
- CFB in ASRSv1.1-SC Hyperactivity/Impulsivity Subscale score by visit
- CFB in CGI-S score by visit
- CGI-C score by visit
- CFB in MADRS Total Score at Week 14/EOS
- CFB in PHQ-8 Total Score by visit
- CFB in HAM-A Total Score at Week 14/EOS
- CFB in GAD-7 Total Score by visit
- CFB in the WPAI:SHP:
 - Absenteeism percentage by visit
 - Presenteeism percentage by visit
 - Work Productivity percentage by visit
 - Regular Activity percentage by visit
- CFB in BRIEF-A T-score at Week 14/EOS for the
 - GEC
 - BRI
 - MI
- CFB in PSQI global score at Week 14/EOS

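### Read literally, the SAP's early-termination mapping rule takes MADRS, HAM-A, BRIEF-A and PSQI records of participants who stop before Week 9 out of the Week 14/EOS endpoint and puts dropout-only points on the MADRS and HAM-A plots

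*SAP*

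**What the plan says.** SAP 5.7 works from visit labels: "data will not be analyzed using visit windows; instead, nominal visits will be used". For participants who stop early it adds "Early termination visits will be mapped to next schedule visit and summarized". The rule applies to visits and does not distinguish between instruments.

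The schedule of events (Protocol Table 1, repeated as SAP Table 2) has post-baseline efficacy visits at Weeks 4, 9 and 14. SIGMA (MADRS), SIGH-A (HAM-A), PSQI and BRIEF-A appear only at Televisit 1b and Week 14/EOS. Their endpoints follow that timing; SAP 7.2 lists, for example, "CFB in MADRS Total Score at Week 14/EOS".

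The protocol nevertheless obtains these scales from dropouts. Section 6.3 says "If participant discontinues early (Early-Termination), perform Week 14 assessments", and Section 10.2 says "If a participant is discontinued for any reason other than lost to follow-up, Week 14 procedures should be completed". Section 6.3 sets a limit: "ClinRO/PRO efficacy assessments should not be administered if participant has not taken daily dose of Qelbree for >7 consecutive days prior".

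SAP 5.1 plans profile plots of mean and mean change: "CFB for AISRS total score, MADRS, HAM-A and GAD-7 will be plotted by visit".

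**The concern.** A participant who stops at Week 3 or Week 7 and completes the early-termination battery has a baseline and a post-baseline MADRS. With a valid AISRS at both times, that participant is also in the Full Analysis Set. Under the mapping rule the MADRS record becomes a Week 4 or Week 9 record, and the endpoint is defined only at Week 14/EOS. The same holds for HAM-A, BRIEF-A and PSQI. SAP 5.6.1 deals with missing items, not missing visits, so no other rule brings these records back.

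Two things are at stake. The Week 14/EOS summaries of mood, executive function and sleep move towards a completer analysis although data from some dropouts were collected. In a single-arm study with 33% expected attrition, that would flatter the result if dropouts improve less. In addition, the MADRS and HAM-A curves would join Week 4 and Week 9 means from people who were leaving to a Week 14 mean that comes mainly from completers. MADRS and HAM-A also define eligibility (inclusion criterion 6) and carry the mood question in the trial's title.

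**Working it through.** **Step 1. Label given to an early-termination record on the four scales, rule read literally**

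| Time of termination | Label under SAP 5.7 | Counted at Week 14/EOS? |
|---|---|---|
| Before Week 4 | Week 4 | No |
| Weeks 4 to 9 | Week 9 | No |
| After Week 9 | Week 14 | Yes |

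No participant still on schedule has these scales at Week 4 or 9, so any value with those labels comes from a dropout.

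**Step 2. The plan's own figure.** SAP 3.6 gives about 750 dosed, 500 completers and 33% attrition. 750 x 0.67 = 502.5, and 500 / 0.67 rounds up to 747, so the figures agree. Planned dropouts: 750 - 500 = 250.

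**Step 3. Share of dropouts leaving before Week 9 (day 63 of 98).** The documents do not give dropout timing for this trial, so it is assumed.

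- Uniform: 63/98 = 64%, about 161 of 250.
- Constant hazard: h = -ln(2/3)/14 per week. By Week 4, 750 x (1 - exp(-4h)) = 82. By Week 9, 750 x (1 - exp(-9h)) = 172. By Week 14, 250. This gives 82 before Week 4, 90 between Weeks 4 and 9, and 78 after Week 9. Share before Week 9: 172/250 = 69%.
- Weibull with F(t) = 1 - exp(-λt^k) and F(98) = 0.33, share = F(63)/0.33. Shape 0.5 (front-loaded) gives 83%, about 208. Shape 2 (back-loaded) gives 46%. The share crosses 50% at a shape of about 1.8.

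Indirect evidence: Protocol 3.2.2 reports 372 dosed and 267 completers in the earlier 6-week adult trial, so 105/372 = 28.2% were lost within 6 weeks. This pools active drug and placebo in another population. It points to early dropout but does not establish the timing here.

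**Step 4. Possible effect on a Week 14/EOS mean (illustration).** The capture rates and mean changes are assumptions; the documents give neither. Capture means the share of dropouts who give an early-termination assessment, set at 25% and 75%. Mean change is -10 in 500 completers and -3 in terminators. Timing is constant hazard. Terminators after Week 9 count at Week 14/EOS under either rule.

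| Capture | Terminators counted, literal rule | Mean, literal rule | Terminators counted, amended rule | Mean, amended rule | Shift |
|---|---|---|---|---|---|
| 25% | 78 x 0.25 = 19.5 | (500 x -10 + 19.5 x -3)/519.5 = -9.7 | 250 x 0.25 = 62.5 | (500 x -10 + 62.5 x -3)/562.5 = -9.2 | 0.5 |
| 75% | 78 x 0.75 = 58.5 | (500 x -10 + 58.5 x -3)/558.5 = -9.3 | 250 x 0.75 = 187.5 | (500 x -10 + 187.5 x -3)/687.5 = -8.1 | 1.2 |

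The records relabelled Week 4 or 9 number 172 x 0.25 = 43 and 172 x 0.75 = 129.

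**The case against.** The best defence is that the rule can be read per instrument. For these four scales the next scheduled visit is always Week 14/EOS. The early-termination instruction sits in the protocol's End of Study section, and the endpoint label names EOS. On that reading nothing is misplaced. The reading is possible, but neither document states it, and SAP 5.7 refers to visits. The text needs a sentence whichever meaning was intended.

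Forward mapping is also sensible for the primary endpoint. AISRS is collected at Weeks 4, 9 and 14, and the rule stops a Day 20 value from being reported as Week 14. That stands, and the point here does not touch AISRS.

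Counting early-termination values at Week 14/EOS has its own weakness. BRIEF-A asks about the last month and PSQI covers a one-month interval. For someone who leaves within the first four weeks (about 82 dropouts under constant hazard, before allowing for capture), the answers can reach back before treatment. That is a real cost, which the fix has to display.

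Finally, the study has no formal hypotheses and no power basis. All four scales are secondary, and for secondary endpoints the nominal t-test is optional. This limits the severity.

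**Conclusion.** The point holds as a gap in the SAP wording with a definite consequence under the literal reading. Early-termination records before Week 9 on MADRS, HAM-A, BRIEF-A and PSQI miss their only endpoint, and the MADRS and HAM-A plots acquire Week 4 and Week 9 points made up of dropouts. It should be fixed. It does not affect the primary endpoint, any error rate or any formal decision.

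A reader might infer more than the documents support:

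- That data from most dropouts are lost. The share before Week 9 is 64% to 69% under uniform timing or constant hazard and higher if dropout is front-loaded, but it rests on assumed timing. It also applies only to dropouts who were assessed. Participants lost to follow-up, or off drug for more than 7 days, give no efficacy data under any mapping.
- That the records are discarded. They would still appear in the data listings; what they miss is the endpoint summary.
- That all four scales get misleading plotted points. SAP 5.1 plots only MADRS and HAM-A among the four. For BRIEF-A and PSQI, which SAP 7.2 lists only at Week 14/EOS, the likely effect is omission from the summary.
- That the result is biased by a known amount. The shift of 0.5 to 1.2 points is an illustration under assumed changes and capture, and its direction depends on terminators improving less than completers.

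**What to change.** Amend SAP 5.7 to say that, for MADRS, HAM-A, BRIEF-A and PSQI, early-termination assessments are summarised under Week 14/EOS. Add a separate row for participants assessed at the actual Week 14 visit. State that no Week 4 or Week 9 summary or plotted point is produced for these four scales, and bring the plot specification in SAP 5.1 into line. The current rule can stay for scales collected at every visit.

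The cost is SAP wording and programming; no new data and no change in trial conduct are needed. The downside is that the EOS mean mixes treatment durations, and for very early terminators the one-month recall of BRIEF-A and PSQI can include time before treatment. The separate Week 14 row and a table footnote should show both.

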**Footnotes:**

1. Virtual televisits will last between 45 to 120 minutes. Consent will occur on or before Telehealth Visit 1a.
2. Administer full/entire RMCH Questionnaire (1 up to 8 items) to biological females at Screening only (if not administered at Televisit #1a, administer at Televisit #1b).
3. Only administer the RMCH mQ5 to FOCPs at Televisit #2, #3, and #4 during Treatment [Week 4, Week 9, and Week 14/EOS, respectively].
4. All medications (especially stimulant or non-stimulant ADHD medications) taken 12 months prior to Screening.
5. BP/PR cuff (and UPT) will be shipped once participant is determined eligible. Prior to taking first dose, participant will measure and record BP/PR and weight (and confirm a negative UPT).
6. Weight will be collected with shoes off. BP/PR will be measured in a seated position. Self-reported by the participant to the study team on Day 1 and thereafter reported during scheduled televisits.
7. Height (with shoes off) will be self-reported to the study team.
8. Participant will need to report time, date, and dose of SM within the study mobile app on Day 1
9. PROs and questions about SM administration method and timing will be completed in the study mobile app.
10. At Week 14 the participant will be required to return all SM to Sponsor for destruction upon confirmation of proper SM accountability.
11. If participant discontinues early (Early-Termination), perform Week 14 assessments; however, ClinRO/PRO efficacy assessments should not be administered if participant has not taken daily dose of Qelbree for >7 consecutive days prior.

	Protocol 812P413	
	Page 30 of 61	Version 2.0

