## **10. Study Completion and Discontinuation**

### **10.1 Study Completion**

Participants that take study medication until Week 14/EOS and complete most study procedures (e.g. safety and ClinROs) by the end of the 14-week treatment period will be

	Protocol 812P413	
	Page 46 of 61	Version 2.0

considered to have completed the study. Participants that choose to discontinue study medication prior to Week 14, will be withdrawn from the study and reasons for discontinuation will be noted in the eCRF.

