8.2. Vital Signs

8.2.1. Absolute Value and Change from Baseline

Change from baseline in vital sign variables (blood pressure, pulse rate and weight) will be calculated for each post-dose visit.

Observed values and change from baseline will be summarized descriptively by visit.

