8.2.2. Shift in Vital Signs

Compared to the reference range, each of the three vital signs variables (diastolic blood pressure, systolic blood pressure and pulse rate) values will be classified as low, normal, high or missing. Shift tables for the change from baseline to all study visits will be summarized using number and percentage of subjects by visit.

Vital sign normal ranges are presented in [Table 1](#).

Table 1. Vital Signs Normal Ranges

Parameter	Low	High
Diastolic blood pressure (mmHg)	60	90
Systolic blood pressure (mmHg)	90	140
Pulse rate	50	100

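### Blood pressure and pulse readings taken more than a week after the last dose can enter the Week 4, 9 or 14 safety tables unmarked

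*SAP*

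**What the plan says.** SAP 5.7 uses nominal visits without analysis windows and adds: "Early termination visits will be mapped to next schedule visit and summarized". It sets no condition on time since the last dose.

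For vital signs, SAP 8.2.1 says "Observed values and change from baseline will be summarized descriptively by visit", and SAP 8.2.2 says "Shift tables for the change from baseline to all study visits will be summarized using number and percentage of subjects by visit". Both use the Safety Population, which SAP 5.3 defines by a single dose. SAP 5.1 has an exclusion rule for unscheduled measurements, which "will be excluded from descriptive statistics performed by visits in summary tables", but no rule for readings taken off drug.

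On data collection, Protocol 10.1 says "Participants that choose to discontinue study medication prior to Week 14, will be withdrawn from the study". Protocol 10.2 adds "If a participant is discontinued for any reason other than lost to follow-up, Week 14 procedures should be completed". The Week 14 list in Protocol 6.3 contains "Report systolic/diastolic blood pressure, pulse rate, and weight", with no last-dose condition. The only off-drug limit is in Protocol 6.2, 6.3, 9.2 and Table 1 footnote 11: "ClinRO/PRO efficacy assessments should not be administered if participant has not taken daily dose of Qelbree for >7 consecutive days prior". It covers clinician-rated and patient-reported efficacy assessments and does not mention vital signs.

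**The concern.** Change in blood pressure and pulse is a declared safety endpoint (Protocol 4), and increases in either are listed among the adverse events of concern (Protocol 9.5.5). A reader will take a Week 9 column of pulse changes as describing people on treatment at about Week 9. Under SAP 5.7 the column can also hold readings from people who stopped more than a week earlier, with no way to tell the two apart.

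If a drug-related rise fades after stopping, these readings pull the mean change and the proportion shifting to high towards baseline. That understates risk, which is the unwelcome direction for a safety table. The people affected are those who stopped, some of them for adverse events. SAP 8.2 plans no maximum post-baseline or any-time outlier table, which a later off-drug reading could not dilute. The by-visit tables are therefore the only planned summaries of measured blood pressure and pulse.

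**Working it through.** **Tracing the rule.**
1. A participant stops drug before Week 14 and is withdrawn (Protocol 10.1).
2. Unless lost to follow-up, they do the Week 14 procedures, including blood pressure and pulse (Protocol 10.2, 6.3).
3. If they are more than 7 days off drug, the efficacy scales are skipped but vital signs are still taken (Table 1 footnote 11).
4. The visit is mapped to the next scheduled visit (SAP 5.7).
5. The reading enters that visit's change and shift tables (SAP 8.2.1, 8.2.2).

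Nothing in either document removes or flags it.

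**The plan's own figure.** SAP 3.6 gives about 750 dosed, 500 completing and 33% attrition. 500/(1 − 0.33) = 746.3, rounded up to 747, and 750 × 0.67 = 502.5. Both agree with the stated figures to within rounding. Early leavers: 750 − 500 = 250.

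**Share of a column that is off drug.** The documents do not give the timing of dropout, the share lost to follow-up or the gap between last dose and early-termination visit. Two assumptions are needed:
- leavers are spread evenly, 250/3 = 83.3 per interval, which leaves 667, 583 and 500 on drug at Weeks 4, 9 and 14;
- a share s of leavers give an off-drug reading and the rest give none.

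Then f = 83.3s / (on-drug n + 83.3s).

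| s | Week 4 | Week 9 | Week 14 |
|---|---|---|---|
| 10% | 8.3/675 = 1.2% | 8.3/592 = 1.4% | 8.3/508 = 1.6% |
| 50% | 41.7/708 = 5.9% | 41.7/625 = 6.7% | 41.7/542 = 7.7% |
| 100% | 83.3/750 = 11.1% | 83.3/667 = 12.5% | 83.3/583 = 14.3% |

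Readings more than 7 days after the last dose are a subset of off-drug readings, so at a given s their share is no larger than shown. If all 250 leavers fell in the last interval, s = 10% would give 25/525 = 4.8% at Week 14, and s = 100% would give 250/750 = 33.3%.

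**Effect on a table.** Column mean = (1 − f) × on-drug mean + f × off-drug mean. If off-drug readings were fully back at baseline, the mean rise would shrink by the fraction f.

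For illustration, Protocol 3.3.1 reports pulse rises above 20 bpm in 29% on drug and 13% on placebo in the earlier adult trial. These are any-time rates, not by-visit rates. Taking 29% on drug and 13% off drug:
- f = 1.6%: 29 − 16 × 0.016 = 28.7%
- f = 14.3%: 29 − 16 × 0.143 = 26.7%

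**The case against.** The strongest reply is that few such readings should exist. Protocol 6.4 places the safety follow-up a week after the last dose, Table 1 allows ±3 days, and arranging that call is a listed task of the Week 14 visit (Protocol 6.3), which early leavers also complete. An early-termination visit run as designed should therefore normally fall within about 7 to 10 days of the last dose, and some leavers will still be dosing. This stands, and it makes the lower rows of s the realistic ones. It does not close the gap: the limit is only implied, and footnote 11 itself provides for early-termination visits after more than 7 days off drug.

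A second reply is that the plan never labels these tables on-treatment, and that summarising every post-dose visit in everyone dosed is a legitimate choice. It is, but neither document states that strategy, and separate display would serve a reader under either one.

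Third, the analysis is descriptive, in a single arm, with self-reported readings. Withdrawals for adverse events have their own table (SAP 8.1), and supporting listings are planned. This lowers the weight but does not mark the readings in the by-visit tables.

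A reader might go further and infer that the tables will in fact understate the drug's effect. The documents do not support that. They give no offset time for blood pressure or pulse, and permitted stimulants and mood medications may continue, so readings off Qelbree need not return to baseline. Nor does the remark about 24-hour exposure in Protocol 3.3.2 justify a 1-day cut-off; it concerns dosing convenience.

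**Conclusion.** The gap is real and minor. Blood pressure and pulse readings taken more than 7 days after the last dose can enter the by-visit change and shift tables unmarked, and would dilute an on-drug rise if that rise fades after stopping.

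The likely size is about 1% to 2% of a column, assuming an even spread of some 250 leavers and an off-drug reading from 10% of them. The 11.1% to 14.3% figures are ceilings: every leaver would have to attend off drug, with none lost to follow-up. The 33.3% figure also needs every leaver in one column. Neither should be read as an expectation.

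The point does not extend to other outputs. The early-termination C-SSRS is the since-last-visit version, whose recall period includes time on drug, so it belongs in its by-visit table. The adverse event tables are not by visit. The primary endpoint is on the AISRS, which is covered by the existing 7-day bar.

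**What to change.** In SAP 5.7 and 8.2, before database lock:
- restrict the by-visit blood pressure and pulse change and shift tables to readings taken no more than 7 days after the last dose, matching the protocol's limit for efficacy scales;
- show later early-termination readings in a separate row, with days since last dose, so that no data are discarded;
- add days since last dose to the vital-signs listing;
- treat any shorter window as an optional sensitivity display only;
- leave the C-SSRS and adverse event tables as they are.

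The cost is a few sentences, one derived variable (reading date minus last-dose date) and one extra table row. The last-dose date is already needed for exposure (SAP 6.6). The weakness is that this date is reported by the participant, since after the first dose dosing information is collected at the televisits (Protocol 6.2); a 7-day limit should tolerate errors in recall better than a 1-day one. No protocol amendment, extra visit or change in sample size is needed.
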